Form B: Medical IRB Research Description

1. **Background:** The Tanglewood Trail walking group is a community-initiated walking group, spontaneously established in summer 2016. Community members meet at the Housing Authority in Whitesburg, KY and walk the approximately 1 kilometer Tanglewood Trail connecting the Housing Authority to the Farmer's Market. Participation in the walking group is open to the public. Participants that walk to the Farmer's Market on Wednesday evenings receive a \$5 voucher to the Farmer's Market and a \$10 voucher on Saturdays during the season (June-October). Adults 18 years and older receive one voucher each time they walk. Currently, there is no evaluation of the walking group program beyond the community tracking the name, number of walkers, and the number of vouchers distributed to walkers on each Wednesday and Saturday. This program was initiated by community members and UK researchers were not involved with its creation or tracking any component of the program.

The current proposed study will target non-pregnant healthy, 18+ years old, community members who are willing and able to walk the Tanglewood Trail on Saturday mornings, June-August 2017. Community members will be randomized into a walking group and a farmers market group. Both groups will receive farmers market vouchers of equivalent value. One group will meet at the Housing Authority and walk to the farmers market to obtain their vouchers and the other group will obtain their farmers market voucher at the farmers market. Both groups are welcome to walk the Tanglewood Trail if they would like, however those that are randomized into the walking group are expected to walk. However, people are not forced to walk and have the option to refuse to walk. We hypothesize that adults who regularly attend the walking group and subsequently purchase fruits and vegetables at the Farmer's Market will experience an increase in physical activity, fruit and vegetable intake, and community engagement, and a decrease in anthropometrics and biomarkers associated with adulthood chronic disease (including cholesterol, hemoglobin A1c, blood pressure, carotenoid status, weight, and waist circumference) beyond that of the farmers market voucher group only.

2. **Objectives:**

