- a) To educate Tanglewood Trail program participants about the health benefits of consuming a variety of fruits and vegetables, being physically active, and dietary strategies that can help protect their health from environmental pollution.
- b) Assess self-reported behavior change, knowledge change, and change in physical measurements (see below), and level of physical activity.

3. **Study Design:** The sample population consists of a convenience sample that is participating in a prospective study. This study will focus on nonpregnant healthy adult (ages 18+) community members who walk the Tanglewood Trail on Saturdays, June-August 2017.

Any interested community members who are 18 years or older, nonpregnant and able to voluntarily give their consent are welcome to join the study. One hundred participants will be randomized into one of two groups – a walking group and a farmer's market group.

The fifty participants randomized into the walking group will meet at the Housing Authority at a designated time each Saturday. When they arrive, they will be signed in by a community leader and receive a farmer's market voucher (**see attached**) for \$10 along with education material (5 of the 13 Saturdays). They will walk as a group to the farmer's market and hand their voucher to the market manager, who will give them \$10 in tokens to purchase fruits and vegetables at the market. The voucher will have two sides: one side will ask participants what fruits and vegetables they ate the past week; the second side will ask participants to check off what fruits and vegetables they purchase at the market that day. They will turn this in as they leave the market. The fifty participants randomized into the farmer's market group will meet at the farmer's market and sign in with a UK employee. They will receive the same voucher and education materials and follow the same procedure as the walking group. Participants randomized into this group will be allowed to walk if they want; no one will be dissuaded from engaging in physical activity. However, in order to receive their voucher, it is not required for them to walk.

Three times per month participants will be presented with education material concerning phytonutrients, the importance of fruit and vegetable intake, and how these factors might protect them from environmental pollutants. The education materials will be in the form of a.) a handout based on the Transtheoretical Model

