Form B: Medical IRB Research Description

(see attached example) or b.) Plate it Up Kentucky Proud recipe samples and cards (see attached example). A Registered Dietitian will be available to answer nutrition-based health questions once per month.

No participants will receive medications – neither real nor placebo.

Data will be a time series collection of finger-stick total cholesterol, LDL, HDL, triglycerides, hemoglobin A1c (cardiocheck meter), height, weight, waist circumference, carotenoid status (carotenoid RS, which is a non-invasive instrument that is a reliable indicator of fruit and vegetable intake (see attached), and a survey (see attached). Measurements will be taken twice – baseline data will be collected in May 2017, with follow-up data collected in early September 2017.

Finger stick tests will be conducted by University of Kentucky employees who have completed all necessary biohazard training (see attached IBC approval and certificates of completion). Lysol wipes will be available to wipe down equipment as needed. Hand sanitizer will be provided to each researcher to use between glove changes. Gloves will be changed between each participant. Heat packets will be available for participants with cold hands to make the finger stick go faster and easier. Lancets will be used to take the finger stick and all materials will be disposed of in sharps containers. All sharps containers will remain sealed until the research team returns to the University of Kentucky that same day to dispose of the sharps containers.

4. **Study Population:** Based on walking group numbers from summer 2016 we anticipate a maximum enrollment of 100 participants (18+ years old, nonpregnant). Previous research in Letcher County suggests the majority of participants will be white, ages 18-65, both male and female, of moderate health status. A prerequisite for participating in this study is the ability to walk approximately 1 kilometer to the Farmer's Market, nonpregnant, pre-supposing a baseline health status. Any interested community members over the age of 18 and in moderate or good health will be included. Since our focus is on changes in rates of chronic disease in adulthood, children will be excluded from study participation (but may walk the trail with their parents). Institutionalized adults, pregnant adults adults with impaired consent capacity, and prisoners will be excluded. No one will be excluded based on sex/gender or racial/ethnic identity.

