7. **Research Procedures:** Following IRB approval, beginning in May 2017 community members will show up to a designated location approximately 1 kilometer from the Farmer's Market. Participants will fill out a survey and have anthropometric and biological measurements taken. Carotenoid status will be measured via carotenoid RS scanner. Anthropometric data will be collected by UK researchers and include weight (digital scale), height (portable stadiometer), waist circumference (tape) and blood pressure (digital blood pressure machine) Finger stick tests will be conducted by University of Kentucky employees who have completed all necessary biohazard training. Lysol wipes will be available to wipe down equipment as needed. Hand sanitizer will be provided to each researcher to use between glove changes. Gloves will be changed between each participant. Heat packets will be available for participants with cold hands to make the finger stick go faster and easier. Lancets will be used to take the finger stick and all materials will be disposed of in sharps containers. All sharps containers will remain sealed until the research team returns to the University of Kentucky that same day to dispose of the sharps containers.

Form B: Medical IRB Research Description

In June through August 2017, participants in the walking group will continue to show up to the same location, be signed in by a community member, and walk approximately 1 kilometer to the Farmer's Market, in exchange for \$10 they can spend at the market. Participants in the farmer's market group will show up to the farmer's market, be signed in by a UK employee, and follow the same voucher protocol as the walking group. Three Saturdays of each month, participants from both groups will receive education material in the form of a.) handouts based on the Transtheoretical Model or b.) Plate it Up Kentucky Proud recipes samples and cards. A Registered Dietitian Nutritionist will be available at least one weekend of each month to answer nutrition-related questions.

Post-data will be collected in September 2017; the same survey will be administered and participants will again have their anthropometric and biological measurements taken.

No clinical care will be given as a part of this research study.

8. Resources:

PI – [name], RDN, LD
 Program Manager – [name], RDN, LD
 Research assistant – [name]
 Undergraduate research assistants
 Community Leader
 Community Stakeholder

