The PI, program manager, and research assistant will be responsible for all data collection and analysis. All education materials will be developed by the program manager and research assistant with oversight by the PI. The program manager and undergraduate research assistants will be USDA Good Agricultural Practices (GAP) trained to serve Plate it Up Kentucky Proud samples at one Farmer's Market per month. Undergraduate research assistants will also assist in data entry as needed (they will complete CITI certification and be added to research personnel list before having access to data). The PI will provide guidance through the process. The PI has space to store all of the consent forms, paper surveys, shopping cards and measurement data sheets in a locked drawer in the PI's locked office. All UK study personnel have computers and statistical analysis software to carry out research procedures, which are all password protected to secure any electronic files that are generated from this study. The PI has funds to purchase paper and food supplies and transportation to conduct the study.

In the event that unanticipated problems or noncompliance issues occur or the situation arises that requires submission of protocol modifications or interim results, the PI will first consult the Office of Research Integrity's website to determine action steps appropriate to the issue. If the PI still has questions she will contact the Office of Research Integrity to obtain the appropriate protocol to resolve a situation.

9. Potential Risks:

No physical, psychological, social, legal, cultural, or financial risks can be perceived from participating in this research. In the rare case that a dangerously high blood pressure or hemoglobin A1c is recorded, the participant will be referred immediately to the local emergency department for care. All foods prepared for the farmer's market will be accompanied by a recipe card with ingredients. Potential allergens will be identified and communicated to all participants. Participants will not be forced to taste any food. Undergraduate research assistants will be GAP trained and knowledgeable about food safety issues. No participants will be discouraged from walking to the farmer's market, regardless of which group they are randomized into. The only difference between the two groups is where they sign in; the walking group signs in 1 kilometer from the market, while the farmer's market group signs in at the market.

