Participants will be asked for finger-stick total cholesterol, LDL, HDL, triglycerides, hemoglobin A1c (cardio check meter), height, weight, waist circumference, and carotenoid status (carotenoid RS, which is a non-invasive instrument that is a reliable indicator of fruit and vegetable intake) twice (May and September 2017).

The collected data will be collated and summarized without identification or attribution to the individual participants. All reports will only reveal aggregated summaries across participants. The surveys with attached consent forms will be collected and stored separately in a locked drawer in the PI's locked office. An electronic document containing participant name and code will be generated and stored on a password protected computer. Following the collection of post-survey data and coding of the post-survey data the electronic document containing the names and codes will be deleted. To minimize risk of identification the consent forms will be removed from the survey and the survey will have a code written on it. The consent forms, shopping cards and surveys will not be stored together, but both will be in a locked drawer.

The information collected will be used to assess whether walking 1 kilometer to the farmer's market and spending approximately \$10 at the market improves physical activity, fruit and vegetable intake, community engagement, and chronic disease-related biomarkers (i.e. cholesterol, A1c, etc).

14. **Confidentiality:** The collated data will only reveal summarized data without identifiable information. The de-identified data will be available electronically and stored on a password protected computer. The electronic document containing names with respective survey codes will be deleted after post-survey data has been collected and therefore will not be stored. The list will be deleted by January 2020. Any study materials and raw data will be retained for 6 years in a locked drawer within a locked office or on a password protected computer. The PI and program manager assigned to the project and involved in data collection will have access to these items.
15. **Payment:** Participants will be offered a farmer's market t-shirt at the baseline data collection time (May 2017) and a \$10 gift card at post-data collection (September 2017) as well as the weekly \$10 voucher to the farmer's market.
16. **Costs to Subjects:** N/A
17. **Data and Safety Monitoring:** N/A the study does not have greater than minimal risk.

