18. **Subject Complaints:** Participants can voice their concerns to the PI, Co-PIs, program manager, or the Office of Research Integrity, which is listed on the consent form.
19. **Research Involving Non-English Speaking Subjects or Subjects from a Foreign Culture:** N/A
20. **HIV/AIDS Research:** N/A
21. **PI-Sponsored FDA-Regulated Research:** N/A

Tanglewood Trail Walking Program in Rural Kentucky 2020 - SAP

A dependent t-test will be used for the difference in survey questions (environmental pollution knowledge, fruit and vegetable intake, and physical activity) between before and after the Tanglewood trail walking program.

When the sample size is 50, a dependent t-test with a 5% two-sided significance level will have 80% power to detect an effect size of 0.4 calculated from previous data.

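### Section 13 asks whether walking plus voucher spending improves outcomes, but only the walking sign-in is randomised, so the voucher and education part rests on uncontrolled May-to-September change.

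*Combined protocol and SAP*

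**What the plan says.** **Stated purpose.** Protocol section 13: "The information collected will be used to assess whether walking 1 kilometer to the farmer's market and spending approximately" 10 dollars there improves activity, diet, community engagement and chronic-disease biomarkers. This is a question about a package: the walk and the spending together.

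**What differs between arms.**
- Section 1: "Both groups will receive farmers market vouchers of equivalent value".
- Section 3, on the market arm: "They will receive the same voucher and education materials and follow the same procedure as the walking group". The same section lets that arm walk if it wishes.
- Section 7: "participants from both groups will receive education material".
- Section 9: "The only difference between the two groups is where they sign in".

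**Timing.** Section 3: "baseline data will be collected in May 2017, with follow-up data collected in early September 2017". Section 1 describes the existing programme's vouchers as given "during the season (June-October").

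**Hypothesis and analysis.** The hypothesis closing section 1 is incremental: people who walk and buy produce should improve more than the voucher-only arm. The SAP plans one analysis, a dependent t-test on three survey outcomes (pollution knowledge, diet, activity) "between before and after the Tanglewood trail walking program". It states 80% power for an effect size of 0.4 with a sample of 50 at a two-sided 5% level. It contains no comparison of arms, no adjustment for season and no caveat about cause.

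**The concern.** Three parts of the plan ask three different questions. Section 1 asks what walking adds to vouchers, section 13 asks whether walking plus spending works, and the SAP asks whether participants changed. The design can answer the first. It cannot answer the voucher half of the second, because no arm goes without the voucher or the education. The third carries no causal meaning on its own.

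If the plan is followed as written, a significant paired test will be the only inferential result available, and section 13 invites reading it as the programme working. Baseline falls before the stated season and follow-up falls inside it. Diet and activity could plausibly rise over that interval with no programme at all.

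**Working it through.** **1. What each comparison estimates.** Write the mean May-to-September change in each arm as a sum of parts:

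- Market arm: season + voucher + education + repeat measurement and other time effects.
- Walking arm: the same parts + the increment from being assigned to walk.

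The difference between arms leaves the walking increment alone, because both arms share the calendar, the voucher and the materials. The change within either arm, or pooled, leaves a sum of several unknowns. Nothing in the design splits that sum. The between-arm test therefore removes season, but it removes the voucher and education effects with it.

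**2. Which outcomes season reaches.** Of the three SAP outcomes, diet and activity have an evident seasonal route. Pollution knowledge does not, but the same survey is given twice (section 7), so its paired change still carries repeat-survey effects. Because both arms get the same materials, there is also little reason to expect an arm difference in knowledge.

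**3. The SAP's own figure.** Inputs from the SAP: n = 50, effect size d = 0.4, two-sided 5%.
- Noncentrality: 0.4 × √50 = 2.83.
- Exact t with 49 df: power 79.2%.
- Normal approximation: Φ(2.83 − 1.96) = 80.7%.

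The stated 80% reproduces for the test it describes.

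**4. Seasonal shift with no programme effect.** The documents give no seasonal figure, so the shift s, in SDs of the paired change, is an assumption. The rejection probability is the same noncentral t calculation with noncentrality s × √n. The nominal rate is 5%.

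| Assumed s | n = 50 | n = 100 (arms pooled) |
|---|---|---|
| 0.1 | 11% | 17% |
| 0.2 | 28% | 51% |
| 0.3 | 55% | 84% |
| 0.4 | 79% | 98% |

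Both columns are shown because the SAP does not say whether its 50 is one arm of the 100 randomised. The 79% entry is the SAP's power figure seen from the other side; it is not separate evidence.

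**5. Power of the between-arm comparison.** Assume 50 per arm (section 3), no dropout, and a between-arm difference of 0.4 SD of change.
- Noncentrality: 0.4 × √(50/2) = 2.00.
- Normal: Φ(2.00 − 1.96) = 51.6%. Exact t: 50.8%.
- Per arm for 80% power: 2 × (1.960 + 0.842)² / 0.4² = 98.1, so 99 (exact t: 100).
- Difference detectable with 80% power at 50 per arm: 0.57 SD (exact t).

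**The case against.** The strongest reply is that the right hypothesis is already in section 1, and that section 13 is one sentence in a section on records and privacy. Objective (b) in section 2 and the SAP speak only of change or difference; neither attributes it to vouchers, and the section 13 sentence does not mention education. That stands in part: the problem is an inconsistency to reconcile, and the design has a valid question. It does not dispose of the point, because the only planned test matches neither the section 1 hypothesis nor the section 13 question.

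A reader might infer more than the documents support:
- *That no effect in this trial can be separated from season.* Not so. Both arms are measured on the same dates, so randomisation isolates assignment to walk. That contrast is diluted because the market arm may walk, but it is not confounded by season.
- *That every outcome is seasonal.* No seasonal route is evident for knowledge. Carotenoid status plausibly is seasonal but is not among the SAP's tested outcomes.
- *That the false-positive rate is known to be near 80%.* It rests wholly on an assumed 0.4 SD shift.
- *That the SAP's power figure is wrong.* It reproduces.

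The dating also needs care. June to October is the existing programme's voucher season and no 2017 market opening date is given. The SAP is headed 2020 while the measurement dates are for 2017. Applying those dates to the SAP's test is an assumption, though the natural one.

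**Conclusion.** The concern holds for the voucher and education components. Their effect has no concurrent comparator and can be seen only as uncontrolled change, mixed with season for diet and activity and with repeat measurement and other time effects for all outcomes. It does not hold for the walking increment, which the randomisation identifies and section 1 already names; there the gap is that the SAP does not test it.

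The design argument needs no numerical assumption. The size does: at n = 50, an assumed seasonal shift of 0.1 to 0.4 SD would raise the chance of a significant paired result from 5% to between about 11% and 79% with no programme effect. This should be corrected, because it changes what the trial may conclude.

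**What to change.** 1. **Section 13.** Replace the purpose sentence so that it matches section 1: the data will assess whether assignment to the walking sign-in adds to vouchers and education that both arms receive equally.
2. **SAP, inferential test.** Make the comparison of change between arms the test of that question, for example follow-up regressed on arm and the baseline value, reported with a confidence interval. The rewording must not be made without this step, or the SAP would have no test for the reworded question.
3. **SAP, paired change.** Keep the paired May-to-September summaries, label them descriptive and uncontrolled, and state that they will not be reported as an effect of the vouchers, the education or the programme.
4. **SAP, power.** Replace the power statement with one for the between-arm test.

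**Cost.** The changes are to wording and analysis; no new data or participants are needed. The sponsor gives up a causal claim for vouchers and education. The 80% figure does not carry over: power is about 51% for a 0.4 SD difference in change with 50 per arm and no dropout, and lower with dropout. Reaching 80% would need 99 to 100 per arm, against the maximum of 100 in total that section 4 expects. Baseline adjustment may recover some precision, but the documents give no baseline-to-follow-up correlation from which to say how much.

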6. **Informed Consent Process:** All study personnel that will obtain consent are listed in Form A. Participants will be told they can decide to stop their participation at any time. The consent form will be read to any study participants with visual issues. UK study personnel will speak to study participants at an appropriate volume to be heard by study participants. Study personnel will ask if they are speaking loud enough, they will tell study participants to let them know when they need to speak up or slow down or repeat a question, and study personnel will be in tune to signs of study participants straining to hear.

Consent will be obtained before physical measurements or survey data is collected. To obtain consent the UK study personnel will ask potential participants if they would like to participate in a research study that involves asking them questions about their health and diet and will also involve education material on phytonutrients, the importance of fruits and vegetables, and how these factors might protect them from environmental pollution. They will be told their participation is completely voluntary, and that they will be randomized into one of two groups. They will be informed that even if they are randomized into the farmer's market group, they are still allowed to walk whenever and however often they like. Those randomized to the walking group will be told that they are expected to walk each Saturday morning, but they will never be forced to walk and will be encouraged to abstain from walking on Saturdays when they do not feel well. They will also be told their survey answers will not be reported individually or with their name, but as anonymous aggregated data. Additionally, they will be told their participation is voluntary and they can withdraw from the study at any time and they do not have to answer any questions that they are not comfortable answering. If the participant agrees the consent form will be given to them and their signature obtained. The participant will be given a copy of an investigator-signed consent form.

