Finger stick tests will be conducted by University of Kentucky employees who have completed all necessary biohazard training. Lysol wipes will be available to wipe down equipment as needed. Hand sanitizer will be provided to each researcher to use between glove changes. Gloves will be changed between each participant. Heat packets will be available for participants with cold hands to make the finger stick go faster and easier. Lancets will be used to take the finger stick and all materials will be disposed of in sharps containers. All sharps containers will remain sealed until the research team returns to the University of Kentucky that same day to dispose of the sharps containers.

11. Benefit vs. Risk: Potential benefits include (but are not limited to) a decreased risk for high blood pressure, high blood glucose, and cardiovascular disease; a decrease in oxidative stress; a decrease in generalized inflammation; an increase in community engagement; an increase in physical activity, and an increase in overall fruit and vegetable consumption.

There is no more than minimal risk to participants in this intervention with the benefits outweighing any risk. There is however, a potential risk of a breach in confidentiality, which is minimal due to the study being voluntary, removing the signed consent form/cover sheet from the coded pre/post surveys, deleting the document containing participant names and codes once the post-survey data has been coded, shredding the cover sheets attached to post-surveys with participants names, using a password protected computer, and storing any hard copies of study-related material in a locked drawer that is in a locked office.

12. Available Alternative Treatment(s): N/A

Form B: Medical IRB Research Description

13. **Research Materials, Records, and Privacy:** Participants will be asked to fill out two surveys (May and September 2017). The surveys contain questions about demographics, self-reported health, physical activity, fruit and vegetable consumption, and community engagement.

Participants will be asked to complete weekly shopping cards that will require them to mark which fruits and vegetables they purchased at the farmer's market and what fruits and vegetables they ate over the past week.

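### The SAP plans and powers only a before/after paired t-test, so no planned analysis compares the two randomised arms

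*Combined protocol and SAP*

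**What the plan says.** Protocol section 1 (Background) expects people who regularly attend the walking group and then buy produce to gain in physical activity and in fruit and vegetable intake, among other outcomes, "beyond that of the farmers market voucher group only". Section 3 (Study Design) sets up the matching design: "One hundred participants will be randomized into one of two groups", fifty in each. On the comparator arm it adds: "They will receive the same voucher and education materials and follow the same procedure as the walking group". Section 6 (Informed Consent Process) gives the intended contrast: "Those randomized to the walking group will be told that they are expected to walk each Saturday morning".

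The SAP is two sentences long. The first reads "A dependent t-test will be used for the difference in survey questions", names pollution knowledge, fruit and vegetable intake and physical activity, and sets the contrast as before versus after the programme. The second gives that same test 80% power with a sample of 50, a two-sided 5% level and an effect size of 0.4, said to come from previous data. Neither sentence mentions arm, group or randomisation, or says whether the test is run in walkers, in each arm or in everyone pooled. The 50 matches one arm.

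**The concern.** The hypothesis is about a difference between arms, and the only planned test is about change over time. From May to September both arms share the voucher, the education material, the growing season and the experience of answering the same survey twice. A paired test in walkers, or in everyone, adds all of these to any effect of walking. Running it separately in each arm does not help, because a significant change in one arm and not in the other is not a test of the difference.

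Followed as written, the analysis makes no use of the randomisation. A significant result would show that responses changed over the summer and could easily be reported as a benefit of walking. A reader could also take the 80% power as applying to the comparison the trial was randomised to make.

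**Working it through.** **Inputs from the documents.** Paired test, n = 50, two-sided 5%, effect size 0.4, 80% power (SAP); 50 per arm (section 3). The 0.4 is read as mean change divided by the SD of change, the natural scale for a paired test.

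**Assumed, because the documents give no figure.** A shift common to both arms of 0.2, 0.3 or 0.4 SD of change; a baseline/follow-up correlation ρ of 0.3 to 0.8; dropout of 0% or 20%; and, for illustration only, 0.4 SD of change as a between-arm difference.

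**1. The SAP's own figure.** Noncentrality = 0.4 × √50 = 2.83 on 49 df, giving power 79.2%. The normal approximation is Φ(2.83 − 1.96) = 80.7%. Exactly 80% power is reached at an effect of 0.404. The stated figure reproduces.

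**2. How often the paired test is significant when walking adds nothing.** With a common shift d, the noncentrality is d√n:

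| Common shift (SD of change) | Paired, 50 walkers | Paired, 100 pooled | Between-arm test |
|---|---|---|---|
| 0.2 | 28% | 51% | about 5% |
| 0.3 | 55% | 84% | about 5% |
| 0.4 | 79% | 98% | about 5% |

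A simulation (20,000 trials, 50 per arm, ρ = 0.5, no group effect) agrees. The between-arm tests, by change score or ANCOVA, rejected in about 5% of trials at every shift.

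**3. What 50 per arm can detect between arms.**

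*Change scores.* Noncentrality = d / √(2/50) = d / 0.2 on 98 df. The difference detectable with 80% power is 0.57 SD of change; the normal approximation is (1.96 + 0.84) × 0.2 = 0.56. At d = 0.4 the noncentrality is 2.0 and power is 51%.

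*ANCOVA.* The SD of change is σ√(2(1 − ρ)) and the residual SD after baseline adjustment is σ√(1 − ρ²). A difference of d SD of change therefore becomes d√(2/(1 + ρ)) residual SDs, tested on 2n − 3 df.

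| | 50 per arm | 40 per arm (20% dropout) |
|---|---|---|
| Detectable, change scores | 0.57 | 0.63 |
| Detectable, ANCOVA, ρ = 0.3 | 0.46 | 0.51 |
| Detectable, ANCOVA, ρ = 0.8 | 0.54 | 0.60 |
| Power at 0.4, change scores | 51% | 42% |
| Power at 0.4, ANCOVA, ρ = 0.3 | 69% | 59% |
| Power at 0.4, ANCOVA, ρ = 0.8 | 55% | 46% |

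Differences are in SD of change. Multiplying by √(2(1 − ρ)) converts them to outcome SDs: the 50-per-arm ANCOVA values become 0.54 at ρ = 0.3 and 0.34 at ρ = 0.8. The 0.4 itself is 0.47 outcome SD at ρ = 0.3 and 0.25 at ρ = 0.8.

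**The case against.** **The SAP may not belong to this design.** It is headed "Tanglewood Trail Walking Program in Rural Kentucky 2020 - SAP", while the protocol describes May to September 2017. It names no arms, and it lists pollution knowledge, which section 13's account of the survey content does not mention. That last sign is weak, since objective (b) includes knowledge change. The doubt is real, but no other design is supplied. If the SAP does not apply, the two-arm study has no analysis plan at all.

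**The SAP fits the stated objectives.** Objective (b) in section 2 is about change. Section 13 states an aim without a comparator: "The information collected will be used to assess whether walking 1 kilometer to the farmer's market", together with spending about $10 there, improves outcomes. The paired test is reasonable for objective (b) and should stay. Neither statement answers the hypothesis in section 1 or explains why participants are randomised.

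**A comparison by assignment is not quite the hypothesis, and the contrast may be diluted.** Section 1 speaks of regular attenders who buy produce. Comparators may walk, walkers may decline, and section 9 describes the sign-in place as the only difference between groups. Comparison by assigned group is still the one that randomisation protects. Dilution leaves the detectable difference unchanged but makes the true difference smaller: at 50 per arm, change-score power is 32% for a difference of 0.3 SD of change and 17% for 0.2.

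**ANCOVA is a preference.** True: a two-sample test of change scores would also close the gap. ANCOVA needs no more data and detects a smaller difference at each correlation considered.

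**Conclusion.** The point holds and needs correcting before analysis. No planned analysis compares the randomised arms on fruit and vegetable intake or physical activity, the two SAP outcomes named in the hypothesis. This rests on the text alone and on no assumed number. The fault lies in the question the test answers; the SAP's arithmetic is sound.

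The size of the problem does depend on the assumptions set out above. A shared summer shift of 0.2 to 0.4 SD of change would make the paired test in walkers significant 28% to 79% of the time with no walking effect. For the between-arm question, an assumed difference of 0.4 SD of change has 51% power by change scores or 55% to 69% by ANCOVA at 50 per arm. Neither range is a corrected version of the SAP's 80%, which belongs to a different test. The one open matter is whether the SAP headed 2020 governs the 2017 two-arm design.

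**What to change.** 1. Confirm that the SAP applies to the two-arm design in sections 1 and 3.
2. For fruit and vegetable intake and for physical activity, make the main analysis an ANCOVA of the September value on randomised group and May value, with participants analysed in their assigned group. Report the adjusted group difference with a 95% CI, and the number without a September value in each arm.
3. Keep the dependent t-test for objective (b), including pollution knowledge. State which participants it covers, and say that it is not to be read as an effect of walking.
4. Label the 80% as belonging to the dependent t-test and add:

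> For the between-arm comparison with 50 per arm, a two-sided 5% level and no dropout, the difference detectable with 80% power is 0.57 SD of change by change scores, or 0.46 to 0.54 SD of change by ANCOVA for an assumed baseline/follow-up correlation of 0.3 to 0.8. With 40 per arm (assumed 20% dropout) it is 0.63, or 0.51 to 0.60 by ANCOVA.

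**Cost.** SAP wording and one regression for each of two outcomes. If the SAP applies to the 2017 design, no visits or enrolment are added, because section 13 already plans May and September surveys. Assigned arm must be kept in the coded dataset, since section 14 has the list linking names to codes deleted. The real price is a less favourable power statement for the comparison of interest.
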